### **10.3 Follow-up:**

- a. Prostatectomy: patients without evidence of  $^{68}\text{Ga}$ -RM2 PET positive nodal or metastatic disease noted on imaging will undergo radical prostatectomy. If a  $^{68}\text{Ga}$ -RM2 PET positive regional pelvic node is noted, the urologist will be informed of the location of the suspicious node and the patient will undergo prostatectomy with nodal dissection.
  - i. Patients with nodes seen on  $^{68}\text{Ga}$ -RM2 PET without positive nodes on pathology, will be rescanned with MRI or CT to determine if the suspicious node was thought to be removed. A  $^{68}\text{Ga}$ -RM2 PET may be repeated as well.
- b. If sites of  $^{68}\text{Ga}$ -RM2 PET positive osseous or distant metastatic lesions are noted, the urologist will be informed, and further evaluation including further imaging (bone scan,  $^{18}\text{F}$  NaF PET, CT or MRI cross section imaging) or targeted biopsy will be performed in order to restage the patient prior to the decision regarding whether or not a prostatectomy will be performed as per the responsible surgeon and standard of clinical care.
- c. The results of this research scan will be provided to the treating physician who may, at their discretion, decide to conduct further imaging scans and/or biopsies. The type and details of these additional scans are not specified, and are at the treating physician's discretion.
- d. Pathology: Specimens from prostatectomy will be evaluated for the presence of nodal metastasis. This will be reported on a per patient basis as positive or negative.
  - i. If possible, the presence of nodal disease on a per region basis (inguinal, left/right obturator, external and internal iliac, paraaortic nodal regions) should be performed. This data will be grouped for subanalysis.
  - ii. The number of nodes counted on pathology will also be recorded.

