## PROTOCOL SYNOPSIS

TITLE	 Ga-RM2 PET/MRI for Detection of Regional Nodal and Distant Metastases in Patients with Intermediate and High-Risk Prostate Cancer
STUDY PHASE	Phase 2
INDICATION	Prostate cancer
INVESTIGATIONAL PRODUCT OR PROCEDURE	 Ga-RM2
PRIMARY OBJECTIVE(S)	To evaluate  Ga-RM2 PET/MRI for detection of regional nodal and distant metastases in patients with intermediate and high-risk prostate cancer scheduled to undergo prostatectomy with lymph node dissection.
SAMPLE SIZE	90 participants
GOALS	To allow the referring physicians in the GU Oncology group to provide their patients a specific molecular imaging test for prostate cancer that is currently used outside of the United States.  To refine the PET/MRI protocols in the setting of initial staging of patients with intermediate and high risk prostate cancers.

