### **3. PARTICIPANT SELECTION AND ENROLLMENT PROCEDURES**

#### **3.1 Inclusion Criteria**

- Older than 18 year-old
- Biopsy proven prostate adenocarcinoma
- Planned prostatectomy with lymph node dissection
- Intermediate to high-risk disease (as determined by elevated PSA [PSA>10], T-stage [T2b or greater], Gleason score [Gleason score > 6] or other risk factors)
- Able to provide written consent
- Karnofsky performance status of ≥50 (or ECOG/WHO equivalent)
- Diagnostic CT or MRI performed within 30 days prior to the Ga-RM2 PET

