## **10. MEASUREMENTS**

### **10.1 Study Endpoints**

#### **10.1.1 Primary endpoint:**

- i. Sensitivity, specificity, positive and negative predictive value of  $^{68}\text{Ga}$ -RM2 PET for the detection of regional nodal metastases compared to pathology at radical prostatectomy on a per patient basis.

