## Appendix: Inclusion/Exclusion Criteria Checklist

Protocol Title:	68Ga-RM2 PET/MRI for Detection of Regional Nodal and Distant Metastases in Patients with Intermediate and High-Risk Prostate Cancer		
Protocol Number:	IRB-40373		
Principal Investigator:	[name]		

Inclusion Criteria – “Yes” must be checked to be eligible (From IRB approved protocol)	Yes	No	Supporting Documentation
1. Older than 18 year-old			
2. Biopsy proven prostate adenocarcinoma			
3. Planned prostatectomy with lymph node dissection			
4. Intermediate to high-risk disease (as determined by elevated PSA [PSA>10], T-stage [T2b or greater], Gleason score [Gleason score > 6] or other risk factors)			
5. Able to provide written consent			
6. Karnofsky performance status of ≥ 50 (or ECOG/WHO equivalent)			
7. Diagnostic CT or MRI performed within 90 days prior to 68Ga-RM2 PET			

Exclusion Criteria – “No” must be checked to be eligible (From IRB approved protocol)	Yes	No	Supporting Documentation
1. Inability to lie still for the entire imaging time (approximately 30 minutes)			
2. Inability to complete the needed investigational and standard-of-care imaging examinations due to other reasons (severe claustrophobia, radiation phobia, etc.)			
3. Any additional medical condition, serious intercurrent illness, or other extenuating circumstance that, in the opinion of the Investigator, may significantly interfere with study compliance			
4. Metallic implants (contraindicated for MRI)			

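### Section 10.3a names nodal dissection only for PET-positive patients, against the synopsis, 3.1 and the checklist, and 10.4b has no class for a PET-negative patient with no nodes examined

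*Combined protocol and SAP*

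**What the plan says.** **Dissection for all.** The synopsis describes the population as "patients with intermediate and high-risk prostate cancer scheduled to undergo prostatectomy with lymph node dissection". Section 3.1 requires "Planned prostatectomy with lymph node dissection", and the appendix checklist repeats it as item 3.

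**Pathology for all.** The primary endpoint (10.1.1) is the accuracy of "PET for the detection of regional nodal metastases compared to pathology at radical prostatectomy on a per patient basis". Section 10.3d says of nodal pathology: "This will be reported on a per patient basis as positive or negative". In 10.4b, a true negative (ii) needs negative nodal pathology and a false negative (iv) needs positive pathology.

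**Surgery by PET result.** Section 10.3a is the only place that sets out surgery by scan result for patients without distant lesions. One sentence begins "Prostatectomy: patients without evidence of" and, after the tracer name, continues "PET positive nodal or metastatic disease noted on imaging will undergo radical prostatectomy". The next, for a PET-positive regional node, says "the urologist will be informed of the location of the suspicious node and the patient will undergo prostatectomy with nodal dissection". Under 10.3b, patients with PET-positive bone or distant lesions are restaged before it is decided whether to operate.

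**Non-evaluable patients.** Section 10.4b.v has two lines. The first covers PET-positive patients whose node was left in place and who lack definitive follow-up. The second covers patients with extrapelvic nodal metastases who have no prostatectomy.

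**The concern.** The two adjacent sentences in 10.3a differ in whether dissection is named, and the difference follows the result of the test being evaluated. Read literally, that ties the reference standard to the index test (partial verification). A false negative exists in the data only if nodes are examined, so every undissected PET-negative patient with nodal disease drops out of the denominator of sensitivity. Sensitivity is part of the primary endpoint and is the quantity on which the sample size rests.

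The gap in 10.4b matters on either reading of 10.3a. A regionally PET-negative patient may have no nodes examined because surgery was done without dissection. Alternatively, under 10.3b, surgery may not have been done because of a bone lesion, which 10.4b.v.2 does not name. Neither patient fits a class. Someone would have to choose between exclusion and true negative with the PET result already known, and that choice moves specificity and negative predictive value (NPV).

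**Working it through.** **Inputs from 10.4a:** 90 patients, 30% node-positive, PET sensitivity 60%. The plan's figure of 90 cannot be reproduced because no alpha, power or test is stated; this point does not depend on it.

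**Assumptions, not in the documents:**
- f, the share of PET-negative patients undissected: 10%, 25% and 50%, for illustration.
- r, nodal risk in undissected relative to dissected PET-negative patients.
- Specificity 90%, needed only in steps 4 and 5.
- All PET-positive patients verified.

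**1. Everyone dissected.** Node-positive 90 × 0.30 = 27; true positives 27 × 0.60 = 16.2; false negatives 27 − 16.2 = 10.8. Sensitivity = 16.2/27 = 60%, the plan's own value.

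**2. Section 10.3a followed literally.** Observed false negatives = 0, so sensitivity = 16.2/16.2 = 100%, whatever the tracer's true performance.

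**3. In between.** Verified false negatives = 10.8(1 − f)/[(1 − f) + f·r]; crude sensitivity = 16.2/(16.2 + verified false negatives).

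| f | r = 1 (equal risk) | r = 0.5 | r = 0 |
|---|---|---|---|
| 10% | 16.2/(16.2 + 9.72) = 62.5% | 16.2/(16.2 + 10.23) = 61.3% | 60% |
| 25% | 16.2/(16.2 + 8.10) = 66.7% | 16.2/(16.2 + 9.26) = 63.6% | 60% |
| 50% | 16.2/(16.2 + 5.40) = 75.0% | 16.2/(16.2 + 7.20) = 69.2% | 60% |

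Excluding undissected patients or coding them negative gives the same sensitivity, because both remove them from the false-negative cell and leave true positives unchanged.

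**4. Effect of the missing class (specificity 90%, r = 1).** There are 90 − 27 = 63 node-negative patients: true negatives 56.7, false positives 6.3. PET-negative patients number 56.7 + 10.8 = 67.5, and true NPV = 56.7/67.5 = 84.0%. At f = 50%:
- Excluded: specificity 28.35/(28.35 + 6.3) = 81.8%; NPV 28.35/(28.35 + 5.4) = 84.0%.
- Coded negative: specificity (56.7 + 5.4)/(56.7 + 5.4 + 6.3) = 90.8%; NPV (67.5 − 5.4)/67.5 = 92.0%.

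**5. What an adjusted analysis can do.** Giving undissected patients the positive rate seen in verified PET-negative patients (a Begg-Greenes calculation) yields 16.2/[16.2 + verified false negatives/(1 − f)]. At f = 50%:
- r = 1: 16.2/(16.2 + 10.8) = 60%, correct.
- r = 0.5: 16.2/(16.2 + 14.4) = 52.9%, too low.
- r = 0: 16.2/(16.2 + 21.6) = 42.9%, too low.
- r = 2: verified false negatives 5.4/1.5 = 3.6, so crude 16.2/19.8 = 81.8% and adjusted 16.2/(16.2 + 7.2) = 69.2%, both too high.

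The adjusted value is therefore right only at equal risk. At f = 100% it is 0/0 and cannot be computed. In 200,000 simulated trials (r = 1, specificity 90%) its standard error was 0.104 at f = 25% and 0.119 at f = 50%, against 0.096 with everyone dissected.

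**The case against.** The strongest reply is that 10.3a is shorthand. Everything else in the document assumes dissection and nodal pathology in every patient, and 10.3a nowhere says that dissection is omitted. A natural reading is that PET-negative patients go on to the surgery already planned, while for regionally PET-positive patients the surgeon is also told where to look. This stands: a reader might infer that the protocol withholds dissection from PET-negative patients and that sensitivity will be inflated, but the documents support neither statement. The two texts diverge, and only one of the two readings produces bias.

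Second, the shares of 10%, 25% and 50% come from no passage and match neither reading of 10.3a, which imply 0% or 100%. That also stands. They illustrate partial adherence and are not a forecast.

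Third, at equal risk the inflation at 10% and 25% undissected (2.5 and 6.7 points) is smaller than the 9.6-point standard error. This is true, but the error runs in one direction whenever undissected patients carry nodal risk. At 50% undissected it reaches 15 points, the whole gain from 45% to 60% that the plan hypothesises.

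Fourth, the calculation assumes that all PET-positive patients are verified, while 10.4b.v.1 removes some. Verification rates may therefore differ by PET result even if everyone is dissected. A rule that triggers an adjustment on any such difference would be wrong; the trigger should be unverified PET-negative patients.

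The reply does not remove the gap in 10.4b, which is there on any reading of 10.3a.

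**Conclusion.** Wrong as written: an internal inconsistency between 10.3a and the synopsis, section 3.1 and the checklist, together with a missing class in 10.4b.

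The effect on sensitivity is conditional. It is zero if everyone is dissected or if undissected patients have no nodal disease. It is total (100% by construction) if 10.3a is applied literally. In the illustrative cases, which assume that all PET-positive patients are verified, 60% becomes 62.5% to 75.0% at equal risk and 61.3% to 69.2% at half risk. Confidence is high on the wording and the missing class, and limited on size, because the documents do not say how many PET-negative patients would go undissected.

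A reader might also take the crude and adjusted sensitivities as bounds on the truth, or the adjusted value as the answer. Neither follows: both are too high if undissected patients carry more risk than dissected ones, and the equal-risk assumption cannot be tested with these data.

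**What to change.** 1. **Reconcile** 10.3a with the synopsis, section 3.1 and the checklist on nodal dissection in PET-negative patients. The surgical rule is the sponsor's to state.
2. **Add to 10.4b.v** that a patient negative for regional nodes on PET with no regional nodes examined is non-evaluable and is not coded true negative. This covers surgery without dissection and no surgery after 10.3b. Record explicitly when no nodes were examined: 10.3d.ii asks for a node count but does not say that a zero is entered when there is no nodal specimen.
3. **Report by PET result** the number and share of patients with nodal pathology, and the node counts. If any PET-negative patients were not verified, state that crude sensitivity is an upper estimate when undissected patients carry any nodal risk. Give one sensitivity analysis that assigns them the positive rate seen in verified PET-negative patients. Say that its assumption is untestable and that it cannot be computed if no PET-negative patient is verified.

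**Cost.** One wording change, one line, one data field and one table. Exclusion shrinks the evaluable PET-negative group: from 67.5 to 60.8, 50.6 or 33.8 at 10%, 25% or 50% undissected (67.5 × (1 − f), specificity 90%). It lowers crude specificity from 90% to 89.0%, 87.1% or 81.8% at equal risk, and it does not itself correct sensitivity. The sensitivity analysis may give a lower and less precise figure.

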### **10.4 Statistical analysis:**

- a. Sample size: 90 patients in total. The power analysis is based on the comparison of sensitivity between conventional imaging and  $^{68}\text{Ga}$ -RM2 PET.
  - i. 30% of intermediate to high-risk patients have nodal metastases at prostatectomy.

- ii. Conventional imaging has a 45% detection sensitivity for nodal metastases on a per patient basis (2).
  - iii.  $^{68}\text{Ga}$ -RM2 PET has a 60% detection sensitivity for nodal metastases on a per patient basis.
- b. Statistical analysis: The sensitivity, specificity, positive and negative predictive value of  $^{68}\text{Ga}$ -RM2 PET for the detection on a per patient basis will be determined using the below criteria:
  - i. True positive patient:
    - 1.  $^{68}\text{Ga}$ -RM2 PET positive for regional nodes; pathology at prostatectomy positive for regional nodes.
    - 2.  $^{68}\text{Ga}$ -RM2 PET positive for regional nodes, pathology negative for regional nodes, imaging after prostatectomy demonstrates node was not removed at surgery, and follow-up biopsy or imaging demonstrates presence of nodal disease.
      - a. Criteria for positive node on follow-up imaging: imaging within 3-12 months, the node decreases by more than 30% (for patients undergoing systemic treatment or focal therapy at this site) or increase by more than 20% in short axis diameter in the absence of treatment (with a minimum of 3 mm in change in size).
  - ii. True negative patient:
    - 1.  $^{68}\text{Ga}$ -RM2 PET negative for regional nodes; pathology at prostatectomy negative for regional nodes.
  - iii. False positive patient:
    - 1.  $^{68}\text{Ga}$ -RM2 PET positive for regional nodes, pathology at prostatectomy is negative, and imaging after prostatectomy demonstrates that node is no longer present.
  - iv. False negative patient:
    - 1.  $^{68}\text{Ga}$ -RM2 PET negative for regional nodes, but pathology at prostatectomy is positive.
  - v. Non-evaluable:
    - 1.  $^{68}\text{Ga}$ -RM2 PET positive for regional nodes, pathology negative for regional nodes, imaging after prostatectomy demonstrates node was not removed at surgery, and no definitive follow-up is available.
    - 2. Patients with extrapelvic nodal metastases will not be included in this analysis if patients do not undergo prostatectomy.

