#### **10.1.2 Secondary endpoint:**

- i. Sensitivity, specificity, negative and positive predictive value for detection of regional nodal metastases in comparison to cross sectional imaging performed contemporaneously with the  $^{68}\text{Ga}$ -RM2 PET.

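### CT/MRI has no reference standard or reclassification rule, and the plan's PET-triggered rules would usually tilt the PET versus CT/MRI comparison towards PET

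*Combined protocol and SAP*

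**What the plan says.** All references are to the combined protocol and SAP.

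- **Primary endpoint (10.1.1).** The accuracy of RM2 PET for regional nodal metastases is assessed "compared to pathology at radical prostatectomy on a per patient basis". No other reference is named there.
- **Secondary endpoint (10.1.2).** The same four accuracy measures are taken "in comparison to cross sectional imaging performed contemporaneously with the" PET. No reference standard is named.
- **Sample size (10.4a).** "The power analysis is based on the comparison of sensitivity between conventional imaging and" RM2 PET.
- **Follow-up (10.3a.i).** Patients with nodes seen on RM2 PET and negative pathology "will be rescanned with MRI or CT to determine if the suspicious node was thought to be removed".
- **Classification (10.4b).** The criteria are introduced for RM2 PET only. Under b.i.2, a PET-positive, pathology-negative patient is a true positive if post-operative imaging shows the node was not removed "and follow-up biopsy or imaging demonstrates presence of nodal disease". Under b.iii the patient is a false positive if the node is gone. Under b.v.1 the patient is non-evaluable if the node remains and there is no definitive follow-up. Under b.ii, a PET-negative, pathology-negative patient is a true negative, whatever CT/MRI showed.

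**The concern.** The plan uses two definitions of nodal disease: pathology in 10.1.1, and pathology plus a follow-up route in 10.4b. Only a positive PET opens the follow-up route. A node seen on CT/MRI but not on PET, and left in place at surgery, is not required to be rescanned and has no specified way to count as disease. It also has no non-evaluable category.

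This matters because PET versus CT/MRI is both a planned endpoint and the stated basis of the sample size. If the 10.4b criteria are carried into that comparison, patients can be added to the diseased group only when PET was positive. Each is a PET true positive, and on a shared reference each is a CT/MRI miss if CT/MRI was negative. A reader could not then separate the performance of the tracer from the effect of the scoring rule.

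**Working it through.** **1. Routes for a pathology-negative patient**

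| RM2 PET | CT/MRI | Rescan required (10.3a.i) | PET status (10.4b) | CT/MRI status |
|---|---|---|---|---|
| positive | positive | yes | true positive, false positive or non-evaluable | not stated |
| positive | negative | yes | true positive, false positive or non-evaluable | not stated |
| negative | positive | no | true negative | not stated |
| negative | negative | no | true negative | not stated |

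The third row is where the two tests are treated unequally. A node seen on both tests does get the rescan.

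**2. Plan inputs (10.4a)**

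- Sample size: "90 patients in total".
- Prevalence: "30% of intermediate to high-risk patients have nodal metastases at prostatectomy", so 90 × 0.30 = 27 node-positive patients.
- "Conventional imaging has a 45% detection sensitivity for nodal metastases on a per patient basis": 27 × 0.45 = 12.15 detected.
- RM2 PET sensitivity 60%: 27 × 0.60 = 16.2 detected.
- Planned gap: (16.2 − 12.15)/27 = 4.05/27 = 15.0 points.

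The total of 90 cannot be reproduced, because no alpha, power or test is stated. That does not affect this point.

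**3. Assumptions**

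Let k be the number of patients reclassified under b.i.2, and c the share of them who were also CT/MRI-positive. The documents give neither. I take k = 1, 3, 5 and c from 0 to 1.

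**4. Formulas**

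- Shared reference (composite for both tests): gap = [(16.2 + k) − (12.15 + ck)]/(27 + k) = [4.05 + k(1 − c)]/(27 + k).
- Mixed reference (composite for PET, pathology alone for CT/MRI): gap = (16.2 + k)/(27 + k) − 12.15/27.
- Pathology alone for both tests: 15.0 points for any k.

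Example, k = 3 and c = 0: PET 19.2/30 = 64.0%, CT/MRI 12.15/30 = 40.5%, gap 23.5 points. On the mixed reference with k = 3: 64.0% − 45.0% = 19.0 points.

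**5. Gap in percentage points (planned: 15.0)**

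| Scoring | k = 1 | k = 3 | k = 5 |
|---|---|---|---|
| Shared, c = 0 | 18.0 | 23.5 | 28.3 |
| Shared, c = 0.45 | 16.4 | 19.0 | 21.3 |
| Shared, c = 1 | 14.5 | 13.5 | 12.7 |
| Mixed | 16.4 | 19.0 | 21.3 |
| Pathology alone | 15.0 | 15.0 | 15.0 |

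**6. Break-even on the shared reference**

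The gap stays at 15.0 points when 4.05 + k(1 − c) = 0.15(27 + k) = 4.05 + 0.15k. This gives 1 − c = 0.15, or c = 0.85 for every k. Below 0.85 the gap widens; above it the gap narrows.

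**7. Two equally sensitive tests**

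If both tests detect 45% against pathology, k = 3 on the shared reference gives PET 15.15/30 = 50.5%. With c = 0, CT/MRI is 12.15/30 = 40.5%, an artificial gap of 10.0 points. The gap is 5.5 points at c = 0.45 and 0 at c = 1.

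**The case against.** The strongest reply is that the plan never says how CT/MRI is scored. Section 10.4b limits itself to RM2 PET and 10.1.2 names no reference. Pathology alone for both tests fits the wording of 10.1.1 and would not have this asymmetry. That stands: the demonstrable defect is a missing rule for the comparator, and the tilt follows only if 10.4b is applied to PET in the comparison. It does not remove the point, because 10.4b contains the only scoring criteria in the plan and nothing in 10.1.2 sets them aside.

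A reader might go further and infer that the comparison is certain to be biased towards PET. The documents do not support this. On a shared reference the gap narrows once c exceeds 0.85, and a high c is conceivable. The rescan is by MRI or CT, and the imaging route in b.i.2 needs a measurable short-axis change of at least 3 mm, so reclassified nodes may tend to be visible on cross-sectional imaging. Against that, visible is not the same as called positive, and biopsy is an alternative route. Section 2 also says the difficulty at initial staging is metastatic nodes too small to meet CT and MRI size criteria, which makes a low c plausible.

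A reader might also infer a specificity bias of known size. Its size, and whether a gap appears at all, depends on the reference chosen for CT/MRI and on overlap between the tests' positive patients. The documents settle neither.

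Section 10.3c allows the treating physician further imaging or biopsy, so a CT/MRI-only node might be followed up. This work-up is discretionary and supplies no scoring rule for CT/MRI.

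**Conclusion.** The concern holds as an unequal and incomplete rule. The rescan, reclassification and non-evaluable provisions start only from a positive PET, and the comparator has neither a reference standard nor an equivalent provision. That much is certain from the text.

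The effect on the result is conditional. If the 10.4b criteria are used for PET in the comparison, they would usually favour it. Over the assumed range of k = 1 to 5, the 15.0-point planned gap becomes 12.7 to 28.3 points on a shared reference. On a mixed reference it becomes 16.4 to 21.3 points, and the two sensitivities then have different denominators (27 + k and 27) and are no longer paired. Neither k nor c can be estimated from the documents.

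The point concerns the secondary comparison and the sample-size rationale. Unequal treatment of the comparator does not alter how PET's own results are classified for the primary endpoint. The plan should be corrected on this point.

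**What to change.** - In 10.1.2 and 10.4, state that the PET versus CT/MRI comparison scores both tests in the same patients against pathology at prostatectomy alone, analysed as paired data.
- Report the composite formed by b.i.2 and b.v.1 only as a supplementary analysis of PET.
- Reconcile 10.1.1 with 10.4b, so that the plan states which reference applies to which analysis.

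**Cost.** Wording only, with no added procedure. A few true nodes left in place would no longer count for PET in the comparison, so its sensitivity would look slightly less favourable there. The supplementary analysis keeps that information.

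**Limit.** Pathology alone is still not fully independent of PET, because under 10.3a the urologist is told where a PET-positive node lies. The change removes the unequal scoring but not that influence, which the report should acknowledge.

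### Section 10.4b lets follow-up reclassify PET-positive men only, so the reported accuracy departs from the pathology reference of 10.1.1 and sensitivity can only move upwards from it

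*Combined protocol and SAP*

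**What the plan says.** Section 10.1.1 defines the primary endpoint as sensitivity, specificity, PPV and NPV of the PET scan "compared to pathology at radical prostatectomy on a per patient basis". No other reference is named there.

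Section 10.4b sorts men as follows.

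- **PET-positive, pathology-negative.** The man is a true positive if "imaging after prostatectomy demonstrates node was not removed at surgery, and follow-up biopsy or imaging demonstrates presence of nodal disease" (b.i.2). The imaging criterion is a change in short-axis size at 3-12 months. He is a false positive only if post-operative imaging shows the node has gone (b.iii.1). He is non-evaluable if "imaging after prostatectomy demonstrates node was not removed at surgery, and no definitive follow-up is available" (b.v.1).
- **PET-negative, pathology-negative.** The true-negative rule reads "PET negative for regional nodes; pathology at prostatectomy negative for regional nodes" (b.ii.1), with nothing further.
- **False negative.** The only route is "PET negative for regional nodes, but pathology at prostatectomy is positive" (b.iv.1).

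Section 10.3 a.i provides post-operative re-imaging only for men with PET-positive nodes and negative pathology. Section 10.3 c allows other scans and biopsies at the treating physician's discretion, but 10.4b does not use them for PET-negative men. The calendar in section 7 lists no follow-up imaging. One-year PSA outcome is exploratory (10.1.3) and does not feed the classification.

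**The concern.** The index test decides which reference standard a man receives. Nodal disease left outside the dissection joins the sensitivity numerator if PET saw it. If PET missed it, the man stays a true negative, even if a biopsy proves the disease within the same year. This is differential verification, and it sits inside the primary endpoint.

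Two things are at stake. First, the figures produced by 10.4b are not those that 10.1.1 describes. Second, with about 27 node-positive men expected, a few reclassified men visibly change the headline sensitivity. Both problems concern PET's own accuracy and exist without any comparator.

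**Working it through.** **Planned counts (10.4a).** 90 x 0.30 = 27 node-positive men and 63 node-negative. At 60% sensitivity, 27 x 0.60 = 16.2 true positives and 10.8 false negatives. The total of 90 cannot itself be reproduced, because no alpha, power or test is stated; this point does not depend on it.

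**Step 1: against pathology alone, the reference in 10.1.1.** Let k be the number of b.i.2 men. The documents do not give k, so k = 1, 3 and 5 are illustrations. Assume also 6.3 other false positives (10% of 63) and no b.v.1 men.

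- Sensitivity: 16.2/27 becomes (16.2+k)/(27+k)
- Specificity: (56.7-k)/63 becomes (56.7-k)/(63-k)
- PPV: 16.2/(22.5+k) becomes (16.2+k)/(22.5+k)
- NPV: (56.7-k)/(67.5-k) under both, because neither true nor false negatives move

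| k | Sensitivity, pathology only / 10.4b | Specificity | PPV |
|---|---|---|---|
| 1 | 60.0% / 61.4% | 88.4% / 89.8% | 68.9% / 73.2% |
| 3 | 60.0% / 64.0% | 85.2% / 89.5% | 63.5% / 75.3% |
| 5 | 60.0% / 66.3% | 82.1% / 89.1% | 58.9% / 77.1% |

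The direction is certain for any k of 1 or more. The size depends on k.

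**Step 2: against true nodal status, equal miss rates.** Let Se = 0.60 be the true sensitivity, f the share of node-positive men whose disease pathology misses (the same in both PET groups), and r the share of missed PET-positive men recovered by b.i.2. Neither f nor r is in the documents; assume f = 5-30% and r = 50-100%.

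Se_obs = Se(1-f+fr) / [Se(1-f+fr) + (1-Se)(1-f)]

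| f | r = 50% | r = 100% |
|---|---|---|
| 5% | 60.6% | 61.2% |
| 10% | 61.3% | 62.5% |
| 20% | 62.8% | 65.2% |
| 30% | 64.6% | 68.2% |

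For example, with f = 20% and r = 100%: 0.60/(0.60 + 0.40 x 0.80) = 0.60/0.92 = 65.2%. False negatives recorded as true negatives number 10.8 x 0.10 = 1.1 at f = 10% and 10.8 x 0.20 = 2.2 at f = 20%.

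If follow-up recovered the same share r in both groups, the factor (1-f+fr) would cancel and the result would be 60%. Pathology alone (r = 0 in both groups) also gives 60%.

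**Step 3: against true nodal status, unequal miss rates.** Let pathology miss a share fp of diseased PET-positive men and fn of diseased PET-negative men.

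- fp = 20%, fn = 0, r = 100%: 0.60/(0.60+0.40) = 60.0%, no bias.
- fp = 20%, fn = 0, r = 50%: 0.54/(0.54+0.40) = 57.4%, reversed.
- fp = 0, fn = 10%: 0.60/(0.60+0.36) = 62.5%, upward with no b.i.2 man at all.

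**Step 4: NPV against true status.** With specificity assumed at 90% (56.7 true negatives), true NPV is 56.7/67.5 = 84.0%. With 1.08 hidden false negatives (f = 10%) the recorded value is 57.78/67.5 = 85.6%; with 2.16 (f = 20%) it is 58.86/67.5 = 87.2%.

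**The case against.** The best defence is that b.i.2 corrects a real weakness of pathology: a node left in the patient cannot appear in the specimen, and calling it a false positive would be unfair to PET. That is reasonable. But it concedes that pathology is imperfect, and nothing in the documents suggests that the imperfection is confined to PET-positive men. Correcting only the misses that PET saw is not neutral.

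Several limits on the criticism stand.

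- A reader might infer that sensitivity is biased upwards in every case. The documents do not support that. Against pathology, it requires at least one b.i.2 man. Against true status, it depends on how misses divide by PET result, and step 3 shows that the bias can vanish or reverse.
- A reader might assume as many missed PET-negative as PET-positive men. A symmetric count would then be 19.2/33 = 58.2% for k = 3 and 21.2/37 = 57.3% for k = 5, gaps of about 6 and 9 points from the 10.4b figures. This is a high-side scenario: it implies that PET finds only half of missed disease, against the planned 60%. With equal miss rates, the hidden false negatives are k x 10.8/16.2, or 2.0 and 3.3. Sensitivity is then 60.0% and the gaps are 4.0 and 6.3 points.
- Setting the shift against the planned difference of 15 points (60% v 45%) is also tempting. It is not like for like, because adding b.i.2 men to the diseased group changes the comparator's sensitivity too.
- The surgeon is told where a PET-positive node lies (10.3 a). This should make unremoved nodes, the only entry to b.i.2, less common. It may also make missed disease relatively more common in PET-negative men, which pushes sensitivity upwards by another route.
- A false-negative rule for PET-negative men cannot restore full symmetry, because no follow-up imaging is scheduled for them and they have no index node to measure.

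**Conclusion.** The point holds in conditional form. Section 10.4b applies different verification according to the PET result and departs from the reference in 10.1.1; nothing elsewhere in the document repairs this. Against pathology alone, sensitivity, specificity and PPV rise with every b.i.2 man and NPV is unchanged. Against true nodal status, sensitivity and NPV are biased upwards if pathology misses disease at similar rates in both PET groups. Under the assumed ranges, the sensitivity bias is about 0.6 to 8.2 points on a true 60%. It could disappear or reverse if misses are concentrated in PET-positive men. The effect is modest, but it lies in the primary endpoint and is cheap to remove from the headline figure, so it should be changed.

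**What to change.** 1. **Primary table.** Report the 2x2 table against pathology at prostatectomy only, as 10.1.1 states. Count b.i.2 and b.v.1 men as PET-positive, pathology-negative.
2. **Second estimate.** Report the 10.4b composite separately and label it as such. Add to b.iv: a PET-negative, pathology-negative man is a false negative if biopsy or imaging done in usual care within the same 12 months shows pelvic nodal disease. Define in advance what counts on imaging, because the b.i.2 size-change criterion presupposes an index node. State that the rule only partly balances verification.
3. **Bounding analysis.** For unverified PET-negative, pathology-negative men, recompute the composite with h hidden false negatives over a stated range: sensitivity = TP/(TP+FN+h) and NPV = (TN-h)/(TN+FN). With k = 3, h = 0, 2 and 3 give sensitivities of 19.2/30 = 64.0%, 19.2/32 = 60.0% and 19.2/33 = 58.2%.

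The cost is SAP wording, one extra table and a short sensitivity analysis; no extra scans are needed. The downside is that some unremoved true nodes count as false positives in the primary table. Reported sensitivity and specificity may be a few points lower. PPV is lower by k divided by the number of PET-positive men: in the step 1 example, 1/23.5 = 4.3 points for one b.i.2 man and 3/25.5 = 11.8 points for three. The pathology-only table uses one reference for everyone, but it does not remove pathology's own misses, so its NPV remains optimistic against true status.
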